### **9.3.5. Accelerometry & Global Positioning System (GPS) logging (child)**

At the end of the initial home visit, the study personnel will provide the participant with their activity belt. The belt will consist of a tri-axial accelerometer (ActiGraph GT3X-BT, ActiGraph Corp., Pensacola, FL, USA) that will be positioned at the right hip, and a passive GPS logger (iTrail H6000, KJB Security Products Inc., TN, USA) that will be either positioned at the left hip of the child, or on the arm of the caregiver. The placement of the GPS logging device will depend on the participant's comfortability with wearing the device on the activity belt, otherwise it is acceptable for the caregiver to wear it on their person. Both the accelerometer and GPS logger will be charged and initialized prior to the home visit. The study personnel will then provide the caregiver with instructions on how the belt is positioned on the child and explain that the child is to wear the belt 24 hours each day. The belt should only be removed during periods of bathing and swimming. As mentioned above, to improve child comfort during the day or while sleeping, the caregiver may remove the GPS device from the pouch attached to the belt at anytime and wear it on their person (a separate, additional belt will be provided to the

caregiver during the initial home visit), so long as they are with their children at all times during the day. Caregivers can remove the belt while sleeping if they find it uncomfortable, but must reattach it each morning.

The accelerometer will objectively measure all movement of the device-wearer continuously. The device is to be worn continuously for 7 days; however, the child can wear the device for 7 days non-consecutively within a 14-day time period if the caregiver identifies that the child is travelling away from home, is ill (e.g., illness that parent perceives as greatly affecting PA, such as fever, major injury, etc.), bedridden, or hospitalized. Accelerometry and GPS data will not be included in analyses during those specified days. This will continue until the caregiver indicates that the participant has returned home from travelling or is no longer ill, bedridden, or hospitalized, when accelerometry collection can resume. Study personnel will gather this information via the daily telephone calls with the participant's caregiver (section 9.3.6).

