### **9.3.6. Daily phone calls (caregiver)**

Every afternoon, study personnel will call the caregiver and go through a daily recall of (a) what time the participant woke up in the morning, (b) if, and when, the activity belt was removed during the participant's waking hours, (c) what time the participant went to sleep, and (d) if the participant left the home during the day (including location and duration away from home). This information will be documented in the Accelerometry & GPS Log each day. If a participant's caregiver cannot be reached on any particular day, study personnel will attempt to call 2 additional times that day. If contact has not been made, study personnel will contact the participant's caregiver the next morning and ask them to recall the previous day, then call again in the afternoon to recall the current day; a normal calling schedule will resume. If contact has not been made within 3 days, which has not been previously agreed upon between the participant's caregiver and study personnel (e.g., the participant is travelling, sick, etc.), the participant will be removed from the study and study personnel will visit the participant's home to collect the activity belt.

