For each child, we will calculate the mean number of minutes per day and the proportions of the child's total eligible wear time that are classified as SED, LPA and MVPA. We will also determine the proportion of days on which each child reached or exceeded 180 minutes of activity classified as LPA or MVPA, and the proportion of days on which each child reached or exceeded 60 minutes of activity classified as MVPA. These cut-offs are based on the Canadian preschooler physical activity guidelines established by Tremblay and colleagues , as there are no Bangladeshi standards available at present. If Bangladeshi guidelines are released before data analysis and reporting is completed, we will also apply those standards in our analyses.

For each child, we will establish the following parameters related to accelerometry:

- Total duration (minutes) of the potential data collection period on all days on which the accelerometer was instructed to be worn;
- Total eligible wear time (minutes), including data collected while the child was awake (from the time that their caregiver indicated that they woke up until the time that they went to sleep). If this data is not provided, total eligible wear time will be measured between 8am and 8pm. Non-wear periods will be excluded based on the following

criteria:  $\geq 20$  minutes of 0 cp15s allowing for up to 2 minutes of 0-100 cp15s in that period. A given day will be considered eligible for inclusion if there are at least 10 hours/day (600 min) between the indicated time period that the child was awake at, or between 8am to 8pm of wear time for those with missing data, after excluding non-wear periods;

- Total indoor eligible wear time (minutes; excluding non-wear periods as previously defined), based on maternal report;
- Total eligible wear time in or around the home (minutes; excluding non-wear periods as previously defined), based on combination of maternal report and GPS logging. "Around the home" will be defined as occurring in the same building or property of the home (e.g., rooftop, neighbouring apartment in the same building, common areas of the apartment building, private courtyard areas that are on the same property as the home in which the child resides).

For purposes of secondary and sensitivity analyses, we will also estimate for each child:

- Mean cp15s for indoor activity
- Mean cp15s for activity in or around the home

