In addition, we will be using the GPS logging data to create ‘heat maps’ for each of the participants’ physical activity locations. This will first be done at the individual level using kernel density estimation and smoothing. These individual ‘heat maps’ can be combined in a master map that will create a visual piece that can aid in describing study findings. We will then use the heat maps for each individual to estimate the average diameter of the ‘sphere’ of activity (km) for the entire study population.

***Objective #2:*** *Estimate the associations between characteristics of the physical environment of the home environment (total area of available floor space inside of the home; frequency that child plays outdoors; number of physical hazards present within the home; number of stationary gross-motor activity-facilitating items present; and number of portable gross-motor activity-facilitating items present) and preschooler activity level.*

To address our second objective, we will first graph each of the variables of interest to assess the data for outliers or implausible data. We will generate histograms, box-plots, and Q-Q plots to assess the following continuous variable:

- Total area of available floor space inside of the home (m^2); Height of stove inside the home (m);

We will generate medians and IQRs for the following discrete, continuous variables:

- Open stairwells in the home (no railing);
- Presence of fine-motor activity-facilitating items;
- Presence of gross-motor activity-facilitating items (for each category).

These discrete, continuous variables may be categorized and treated as categorical variables depending on the data. To assess the linearity between these continuous exposures and outcome measure (using each parameter defined in Section 10.1.), we will create scatterplots and generate the correlation coefficient (Pearson correlation) for each relationship. A locally weighted scatterplot smoother (LOWESS) technique will also be used to check for departures from linearity. If the association between the exposure and the outcome is linear, we will proceed with the linear regression. However, if the association is non-linear, we will proceed with a linear spline model.

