#### **10.4.2. Sensitivity analyses**

To account for the participants' 'adjustment time' to wearing the activity belts, we will exclude the first day of wear-time from analyses.

We will be comparing the wear-time location data from parent-report measures to the data from the GPS logger to evaluate whether parent-report alone provides enough information on the participant's location information. We will assess the GPS data for each participant, specifically looking for substantial coordinate (latitude and longitude) changes. Any deviations from the home coordinates will be cross-referenced to the mother's report by comparing the coordinate's corresponding time stamp and the time indicated by the mother. We will also assess any coordinate changes if the parent indicated that the child left the home.

We will run the same model described in objective 2, however we will stratify by preschooler sex.

We will be comparing the mean cp15s of the Trost and colleagues cut-points to the cut-points established by Pate and colleagues, Sirard and colleagues, and Van Cauwenberge and colleagues. We will conduct an ANOVA to establish if there is a difference among strata listed above.

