## **13. Risks**

This is a minimal risk study. There is a low risk of infection following the collection of hemoglobin concentration via finger prick; appropriate study procedures, including the proper cleaning of the finger using an alcohol swab will help to minimize this risk.

The only potential risk/discomfort associated with wearing the accelerometer and GPS logger is the minimal discomfort and weight of the activity belt. During the daily phone calls, study personnel will ask the caregiver of the participant if there are any problems or concerns with their child wearing the devices. This ensures that if there are any compliance issues surrounding wearing the devices, study personnel will be aware of this immediately. If a participant feels uncomfortable wearing the accelerometer, the study personnel will inform their supervisor, and make appropriate changes to increase compliance and decrease participant burden (e.g., encouraging the participant to wear the belt over/under clothes, depending on preference;

attaching stickers to the devices to make them more visually appealing to children; providing the caregiver with a pedometer to model in front of the child while they wear the activity belt). If after making appropriate changes, the participant still does not feel comfortable wearing the activity belt, they can choose to opt-out of the remainder of the study and still receive compensation, if a minimum of 4 days of accelerometer data collection has been obtained.

If a participant feels uncomfortable wearing the GPS logger specifically, we will allow for the caregiver (or whoever is supervising the child) to carry the device on their person, so long as they are with the child during waking hours. In addition, if the caregiver does not feel comfortable disclosing specific locations that their child visits, they can opt to remove the GPS logger from the pouch attached the activity belt for that specific time period. The device will then be returned to the pouch once the participant has left that specific location.

Research ethics approval will be obtained from both the Research Ethics Board at the Hospital for Sick Children in Toronto and the Research Review Committee and Ethical Review Committee at icddr,b in Dhaka.

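### Caregivers may take the GPS logger out for privacy, but the plan specifies no record of when and no rule to treat those intervals as missing location data

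*Combined protocol and SAP*

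**What the plan says.** Section 13 (Risks) gives a caregiver who is uneasy about disclosing a place this option: "they can opt to remove the GPS logger from the pouch attached the activity belt for that specific time period". It continues: "The device will then be returned to the pouch once the participant has left that specific location". It asks for no time or note of the removal, and it does not say whether the logger is carried, switched off or left somewhere in the meantime.

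Section 9.3.6 lists four items for the daily call: wake time, belt removal, sleep time and trips. The removal item asks "if, and when, the activity belt was removed during the" child's waking hours, so it concerns the belt as a whole. The trip item asks "if the participant left the home during the day (including location and duration away from home"). Neither covers removal of the logger alone. Section 13 adds a general question about problems with the devices, but this is not a record of times.

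GPS data are used in three places:

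- Section 10.1 derives "Total eligible wear time in or around the home (minutes; excluding non-wear periods as previously defined), based on combination of maternal report and GPS logging", and Section 10.4.1 repeats the Objective 1 analyses on that restricted wear time.
- Section 10.4.1 builds individual heat maps and will "use the heat maps for each individual to estimate the average diameter of the ‘sphere’ of activity (km) for the entire study population".
- Section 10.4.2 compares parent report with GPS "to evaluate whether parent-report alone provides enough information on the participant's location information".

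None of these sections says what happens to intervals when the logger was not with the child.

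**The concern.** GPS serves as the yardstick for parent report, yet the same caregiver controls both. The stated reason for taking the logger out is reluctance to disclose a place, and that reluctance could also affect what is said on the telephone. Errors in the two sources may therefore coincide, and the comparison would not show it.

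At stake is the answer to the Section 10.4.2 question, which could support using parent report alone for location. The home-restricted activity summaries, the heat maps and the activity diameter could also carry coordinates that are not the child's. Removal times that are not collected cannot be recovered at analysis.

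**Working it through.** The plan states no figure on this point, so there is none to reproduce. The check is a reading of the sections together, followed by an illustration on assumed values.

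**1. Can any other rule detect the removal?** No. The accelerometer non-wear rules in Sections 10.1 and 9.3.6 depend on counts or on belt removal. If only the logger comes out, the belt stays on and the time remains eligible wear time.

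**2. What does the GPS file show during a removal?** The logger takes a reading every 15 seconds (Section 9.3.5). There are three possibilities:

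- Carried along: the trace continues and records the place.
- Switched off: the trace has a gap.
- Left elsewhere: the trace shows coordinates that are not the child's.

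The documents do not say which occurs.

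**3. What does Section 10.4.2 then find?** It has two checks. One starts from GPS departures from home and looks for a matching report. The other starts from reported trips and looks at the coordinates. For an outing that leaves no GPS departure:

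- Not reported: neither check is triggered, and parent report looks better than it is.
- Reported: the second check finds no matching movement, which looks like a parent error or a logger fault although the report was correct.

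Without removal times, the analyst cannot tell either case from ordinary agreement or ordinary error.

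**4. Illustration.** All inputs are assumptions; none is in the documents.

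- h = share of outings that leave no GPS departure because the logger was removed: 5%, 10%, 20%
- r = parent reporting rate when the logger is with the child: 0.90
- q = parent reporting rate when it is removed: 0, 0.20 or 0.90
- Parents report no outing that did not happen.

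Formulas:

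- Apparent sensitivity of parent report against GPS = r
- True sensitivity = (1 − h)r + hq
- Share of reported outings that GPS confirms = (1 − h)r / [(1 − h)r + hq]

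Example for h = 0.10, q = 0.20: true sensitivity = 0.90 × 0.90 + 0.10 × 0.20 = 0.83; share confirmed = 0.81 / 0.83 = 97.6%.

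| q | h | Apparent sensitivity | True sensitivity | Reported outings confirmed |
|---|---|---|---|---|
| 0 | 5% | 90% | 85.5% | 100% |
| 0 | 10% | 90% | 81.0% | 100% |
| 0 | 20% | 90% | 72.0% | 100% |
| 0.20 | 5% | 90% | 86.5% | 98.8% |
| 0.20 | 10% | 90% | 83.0% | 97.6% |
| 0.20 | 20% | 90% | 76.0% | 94.7% |
| 0.90 | 5% | 90% | 90% | 95% |
| 0.90 | 10% | 90% | 90% | 90% |
| 0.90 | 20% | 90% | 90% | 80% |

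Apparent sensitivity is the same in every row. If removed-logger outings are never reported, sensitivity is overstated. If they are reported as often as others, sensitivity is right but correct reports are counted as unconfirmed.

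**The case against.** Several points on the other side are sound and limit the finding.

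- **Caregiver carriage is not separation.** Section 9.3.5 says "the caregiver may remove the GPS device from the pouch attached to the belt at anytime and wear it on their person", but makes this conditional on the caregiver being with the child during the day, and Section 13 repeats the condition for waking hours. Under the plan such a logger still follows the child. Only the privacy removal lacks that condition. This stands.
- **A removal need not hide the outing.** If the logger comes out only at the place itself, travel there and back may still show as a departure from home, and Section 10.4.2 would cross-reference it. If it is switched off, the result is a gap. This stands, and it is why the direction of any error is unknown.
- **The comparison works both ways.** A caregiver may withhold the place but still report leaving home, and the second check would then raise a discrepancy. True, but without removal times its cause cannot be identified.
- **A reader might infer that no record is kept at all.** The Accelerometry & GPS Log form is not in the documents, so one can say only that none is specified.
- **A reader might infer that the plan counts undisclosed outings as agreement and as time at home, so that parent report would score perfectly.** The documents do not support this. They do not say the logger is left at home, Section 10.4.2 defines no agreement score, and Section 10.1 gives no algorithm for combining the two sources. The fault is silence, not a specified misclassification.

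**Conclusion.** The gap is real and narrow. The plan allows privacy removals, its described call items do not capture them, and no rule makes those intervals missing. In them the GPS may not show the child's location, so the Section 10.4.2 comparison cannot distinguish a shared miss from a correct report without a trace. Wear time in or around the home, the heat maps and the activity diameter may be misclassified as well. A downward bias in the diameter, which a reader might expect, would require the undisclosed places to extend the child's range; nothing in the documents shows this.

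The size cannot be fixed from the documents. The illustrated differences of 0 to 18 percentage points in sensitivity (90% − 72.0% at the extreme) depend entirely on the assumed h, r and q. The primary measure, overall mean counts per 15 seconds, does not use GPS and is unaffected. This is an inexpensive improvement to secondary location analyses, not a threat to the main result.

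**What to change.** - **Collection (Section 9.3.6):** keep the privacy option and add one daily-call item for the start and stop times of any period when the logger was not with the child. Ask for no place.
- **Analysis (Sections 10.1, 10.4.1 and 10.4.2):** treat those intervals as missing GPS in the parent-report comparison, wear time in or around the home, heat maps and activity diameter.
- **Reporting:** give their share of eligible wear time. State that the comparison applies only to time when the logger was with the child, and that unreported removals remain undetected.

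The cost is one more question on an existing call, a filter in the GPS processing, and some wear time left unclassified for location. The correction is partial because it relies on the same caregiver's report. Planned data collection began in August 2017 and the latest listed version is dated April 25, 2018; for any child measured without this item, only the stated limitation can be applied.

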## **14. Benefits**

Although there are no major health benefits for participating in the study, there is an opportunity to receive medical treatment to individuals who are below the hemoglobin concentration cut-off for anemia.

Additionally, all participants will receive a graphics-based, child-friendly activity report of their data collected from wearing the accelerometers (e.g., average number of daily steps taken, average time spent being active, average time spent being sedentary, etc.). All activity reports will congratulate the participants on their achievements throughout the week and thank them for participating in the study. The activity reports will be hand delivered to the participants after the accelerometry data has been analyzed. This will also be explained to caregivers to provide them with additional information on increasing or maintaining their child's physical activity levels to promote optimal health.

Financial compensation will be provided to caregivers for their time and participation in the study, with a minimum of 4 days of activity data collection.

## **15. Safety and Adverse Events**

Adverse events are not predicted to occur in this study.

## 17. Appendix

Table 1 - List of exposure variables and their derivation

Variable	Unit/Categories; Type of variable	Derivation
Total available floor space inside the home	m  ; continuous	
Data required (Form 3: Q9b-c):
 
 
• Averages of the 2 length measures from each room/space inside the home (m)
 
• Averages of the 2 width measure from each room/space inside the home (m)
 
• Averages of the 2 length measures from each large piece of furniture (>1m^2) from inside the home (m)
 
• Averages of the 2 width measure from each large piece of furniture (>1m^2) from inside the home (m)
 
 
Area of each room/space within the home will be calculated by multiplying the averages of the 2 length by width measures for each room/space in the home (m^2). Area of each large piece of furniture within the home will be calculated by multiplying the averages of the 2 length by width measures for each large piece of furniture in the home (m^2). Areas from any beds will also be calculated and identified.
 
The total area of available space indoors (m^2) will be calculated by summing all of the areas of living space dimensions within the home. The total area of large furniture (m^2) will be calculated by summing all of the areas of furniture obstructions within the home, excluding the areas from any beds.
 
Finally, the area of total available floor space inside of the home (m^2) will be calculated by subtracting the total area of large furniture (m^2) from the total area of available space indoors (m^2). Areas of the beds will be included as available indoor floor space, as they are often used as a play area for children in this setting.

Total available floor space inside and	m  ; continuous	
Data required (Form 3: Q11b-c):
 
 
• Area of the total available floor space inside the home (as described above);
 


outside of the home
		
 
• Averages of the 2 length measures from each enclosed space outside the home (m)
 
• Averages of the 2 width measure from each enclosed space outside the home (m)
 
• Averages of the 2 length measures from each large obstruction (>1m^2) within the enclosed space outside of the home (m)
 
• Averages of the 2 width measures from each large obstruction (>1m^2) within the enclosed space outside of the home (m)
 
 
Area of the enclosed outdoor space will be calculated by multiplying the averages of the 2 length by width measures for each outdoor space (m^2). Area of each large obstruction outdoors will be calculated by multiplying the averages of the 2 length by width measures for each large obstruction within the enclosed outdoor space (m^2).
 
The total area of enclosed outdoor space (m^2) will be calculated by summing all of the averages of enclosed outdoor space. The total area of large obstructions (m^2) will be calculated by summing all of the areas of large obstructions within the enclosed outdoor space outside of the home. Finally, the area of total available floor space outside of the home (m^2) will be calculated by subtracting the total area of large outdoor obstructions (m^2) from the total area of enclosed outdoor space (m^2).
 
Finally, the summation of the total available floor space inside of the home (m^2) and the total available floor space outside of the home (m^2) will provide the total available floor space inside and outside of the home (m^2).

Total number of physical hazards in or around the home
	
Count (all integers between 0 and 5); discrete
	
Data required:
 
 
• Presence of unsafe stairwell (No = 0; Yes = 1)             
 
○ Form 3: Questions 12a, 12b, 12c, and 12d
 
○ “No” (will receive a score of 0) if:                 
 
▪ Q12a = 1
 
 
 
 
 

		
 
 
 
▪ Q12a = 2; Q12b = 2; Q12c >0.9 m; Q12d = 1
 
▪ Q12a = 2; Q12b = 2; Q12c >0.9 m; Q12d = 2
 
 
 
○ “Yes” (will receive a score of 1) if:           
 
▪ Q12a = 2; Q12c <0.9 m; Q12d = 1
 
▪ Q12a = 2; Q12c <0.9 m; Q12d = 2
 
▪ Q12a = 2; Q12c >0.9 m; Q12d = 1
 
 
 
● Presence of stove that is accessible to child (No = 0; Yes = 1)           
 
○ Form 3: Questions 13a and 13b
 
○ “No” (will receive a score of 0) if:               
 
▪ Q13a = 1
 
▪ Q13a = 2; Q13b >0.9 m
 
 
 
○ “Yes” (will receive a score of 1) if:               
 
▪ Q13a = 2; Q13b <0.9 m
 
 
 
 
 
● Presence of unfinished construction (No = 0; Yes = 1)           
 
○ Form 3: Question 14
 
○ “No” (will receive a score of 0) if:               
 
▪ Q14 = 1
 
 
 
○ “Yes” (will receive a score of 1) if:               
 
▪ Q14 = 2
 
▪ Q14 = 3
 
 
 
 
 
● Presence of uncovered sewage drain, accessible to the child (No = 0; Yes = 1)           
 
○ Form 3: Question 15
 
○ “No” (will receive a score of 0) if:               
 
▪ Q15 = 1
 
 
 
○ “Yes” (will receive a score of 1) if:               
 
▪ Q15 = 2
 
 
 
 
 
● Presence of boti in home and storage of item is accessible to the child (No = 0; Yes = 1)           
 
○ Form 3: Questions 16a and 16b
 
○ “No” (will receive a score of 0):               
 
▪ Q16a = 1
 
▪ Q16a = 2; Q16b = 2
 
 
 
○ “Yes” (will receive a score of 1):
 
 
 

--	--	--------------------------------------------------------------------------------------------------------------------------------------------------------------------------------------------------------------------------------------------------------------------------------------------------------------------------------------------------------------------------------------------------------------------------------------------------------------------------------------------------------------------------------------------------------------------------------------------------------------------------------------------------------------------------------------------------------------------------------------------------------------------------------------------------------------------------------------------------------------------------------------------------------------------------------------------------------------------------------------------------------------------------------------------------------------------------------------------------------------------------------------------------------------------------------------------------------------------------------------------------------------------------------------------------------------------------------------------------------------------------------------------------------------------------------------------------------------------------------------------------------------------------------------------------------------------------------------------------------------------------------------------------------------------------------------------------------------------------------------------------------------------------------------------------------------------------------------------------------------------------------------------------------------------------------------------------------------------------------------------------------------------------------------------------------------------------------------------------------------------------------------------------------------------------------------------------------------------------

		
 
▪ Q16a = 2; Q16b = 1
 
 
Each score from each of the 5 categories will be added to calculate the combined total of hazards present in the home.

Total number of stationary gross-motor activity items	Count (all integers between 0 and 10); discrete	
Data required:
 
 
• Form 3: Questions 17b-c, 18b-c, 19b-c, 20b-c, 21b-c, 22b-c, 23b-c, 24b-c, 25b-c, 26b-c
 
• The number of incidences where both the 'b' question = 2 AND the 'c' section = 2 (e.g., 17b = 2 AND 17c = 2, this indicates that this item is a stationary gross-motor activity item)
 
 
The number of items that satisfy the above rules will be added together to provide this score. The minimum score is 0 items, with a maximum score of 10 items.

Total number of portable gross-motor activity items	Count (all integers between 0 and 10); discrete	
Data required:
 
 
• Form 3: Questions 17b-c, 18b-c, 19b-c, 20b-c, 21b-c, 22b-c, 23b-c, 24b-c, 25b-c, 26b-c
 
• The number of incidences where both the 'b' question = 1 AND the 'c' section = 2 (e.g., 17b = 1 AND 17c = 2, this indicates that this item is a portable gross-motor activity item)
 
 
The number of items that satisfy the above rules will be added together to provide this score. The minimum score is 0 items, with a maximum score of 10 items.

Hemoglobin concentration	g/L; continuous	Hemoglobin concentration data collecting in Form 4: Q24.

Table 2 - List of additional continuous covariates and their derivation

Variable	Unit	Derivation
Body mass index (BMI) (caregiver)	kg/m 	
Data required (Form 2: Q10-13):
 
 
• Height (m; average of 2 closest height measures)
 
• Weight (kg; average of 2 closest weight measures)
 
 
BMI will be calculated using the formula:  <math>BMI = \text{weight}/\text{height}^2</math>

Body mass index (BMI) z-score (child participant)
	
(z-score)
	
Data required (Form 2: Q1-4):
 
 
• Height (m; average of 2 closest height measures, value will be adjusted by subtracting 0.7 cm if recumbent length was measured)
 
• Weight (kg; average of 2 closest weight measures)
 
 
Height and weight will be plotted on the WHO body mass index-for-age (BMI-for-age) chart (sex specific; ages 2 to 5 years) to determine participant BMI z-score.

Waist circumference
	
cm
	
Average of the 2 closest waist circumference measures (Form 2: Q5,6,14,15)


Body fat percentage (female caregiver)
	
%
	
Data required (Form 2: Q10, 11, 12, 13, 17, 18):
 
 
• Height (m; average of 2 closest height measures)
 
• Weight (kg; average of 2 closest weight measures)
 
• Resistance (ohms measured at 50 kHz; average of the 2 closest resistance measures)
 
 
1) Total body water (TBW; kg) will be calculated using the following equation:  <math>TBW = 4.297 + 0.190 * Weight + 0.349 * Height^2 / Resistance</math>
 
2) To determine fat free mass (FFM; kg), TBW will be divided by a hydration factor of 0.732.
 
3) Fat mass (FM; kg) will be calculated by subtracting FFM from total weight.
 
4) Body fat percentage will be calculated using the following formula: <math>Body\ fat\ \% = (FM / Weight) * 100\%</math>

Body fat percentage (child participant)
	
%
	
Data required (Form 2: Q1, 2, 3, 4, 7, 8):
 
 
• Height (m; average of 2 closest height measures, value will be adjusted by subtracting 0.7 cm if recumbent length was measured)
 
• Weight (kg; average of 2 closest weight measures)
 
• Resistance (ohms measured at 50 kHz; average of the 2 closest resistance measures)
 
 
1) Total body water (TBW; kg) will be calculated using the following equation:  <math>TBW = 0.76 + 0.18 * Height^2 / Resistance + 0.39 * Weight</math>
 
2) To determine fat free mass (FFM; kg), TBW will be divided by a hydration factor of 0.775 (males) or 0.779 (females).

		
3) Fat mass (FM; kg) will be calculated by subtracting FFM from total weight.
 
4) Body fat percentage will be calculated using the following formula: <math>\text{Body fat \%} = (\text{FM}/\text{Weight}) * 100\%</math>

Number of children living in the home	Any integer	
Data required:
 
 
Form 3: Question 3
 

Household density	People/ m 	
Data required:
 
 
Number of adults living in home (Form 3; Question 2)
 
Number of children living in home (Form 3; Question 3)
 
Total available floor space inside of the home (m^2, see above in Table 1)
 
 
The total number of individuals living in the home will be calculated by summing the number of adults living in the home with the number of children living in the home. The total number of individuals living in the home will then be divided by the total available floor space inside of the home to determine household density.

Number of rooms in home	Any integer	
Data required:
 
 
Form 3: Question 4
 

Number of screens available to child	Any integer	
Data required:
 
 
Form 3: Question 8
 

*Table 3 - List of additional categorical covariates and their derivation*

Variable	Categories	Derivation
Sex	Male; Female	Screening Form.
Maternal education	No schooling; some or completed primary education; some or completed secondary education; some or completed tertiary education	
Data required:
 
 
Form 1: Q3-4
 

Household wealth	Wealth quintiles	Information on household characteristics and ownership of specific household items will be collected in Form 1. Using principle analysis, participants will be categorized into 5 separate categories. The first principle component will be used to assign each

		
individual an asset score, with lower scores reflecting ownership of fewer items (i.e., less relative wealth) and higher scores indicative of greater relative wealth. Using the distribution of asset scores in the study population, quintiles will be formed and participants will be categorized appropriately.


Food security status
	
Food secure; moderately food insecure; severely food insecure
	
Data required:
 
 
• Question 18 (Form 4; 1-item food insecurity screening tool; NutriSTEP™)
 
 
A score of 4 indicates food secure; a score between 2-3 indicates moderately food insecure; a score of 1 indicates severely food insecure.
 
 
• Question 19 & 20 (Form 4; 2-item food insecurity screening tool; Hager and colleagues, 2010)
 
 
A combined score of 6 indicates food secure; a combined score of 4-5 indicates moderately food insecure; a combined score of 1-3 indicates severely food insecure.

More than 1 family living in the home
	
Yes; No
	
Data required:
 
 
• Form 3: Question 6a
 

